2 STUDY OBJECTIVES

2.1 Primary

- To evaluate the efficacy of BHV-3241, compared to placebo, as measured by a change from baseline in a modified Unified MSA Rating Scale (UMSARS), consisting of a subset of items from Part I and Part II, at Week 48.
- To assess the safety and tolerability of BHV-3241, relative to placebo, in subjects with MSA.

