3 STUDY ENDPOINTS

3.1 Primary

- Change from baseline in a modified UMSARS score, based on a subset of items from Part I and II, at Week 48 (see Section 9.4.2).
- The frequency of unique subjects with: serious adverse events; adverse events leading to discontinuation; adverse events judged to be related to study medication; clinically significant ECG abnormalities and clinically significant laboratory abnormalities.

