9.4.7 Analysis of Safety

The Investigators determine the intensity of AEs and the relationship of AEs to study therapy. The Investigators' terms are coded and grouped by system organ class using the latest version of the Medical Dictionary for Regulatory Activities (MedDRA) available. AEs will be presented by system organ class and preferred term, ordered by the overall frequency of events. If a subject had an adverse event with different intensities over time, then only the greatest intensity is reported.

AEs are tabulated in all treated subjects. All deaths and SAEs are listed for enrolled subjects without regard to onset.

The frequencies of the following safety events are summarized by treatment group and overall for treated subjects: SAEs; all AEs, non-serious AEs; AEs by intensity; AEs by relatedness and clinically relevant laboratory abnormalities.

Graphical and tabular displays of on-treatment liver function test results are provided.

Safety will be presented separately for the double-blind phase and for the open-label extension phase, overall and by randomized arm.

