3.2.1 Primary Objective Estimand

The estimands corresponding to the primary objectives for this study are shown in Table 1.

Table 1: Primary Objective Estimands

Objective	To evaluate the efficacy of Verdiperstat, compared to placebo, as measured by a change from baseline in a modified UMSARS score at Week 48
Efficacy Endpoint	Change from baseline in a modified UMSARS score at Week 48
Summary	Using the mITT population:
	 Descriptive statistics for modified UMSARS score and change from baseline as a continuous variable by treatment group at each visit
	 Difference in mean change from baseline in modified UMSARS scores between treatment groups at week 48 estimated and tested using a mixed-effect model for repeated measures (MMRM)
Intercurrent	1) Main Analysis - Observed data only
Events	2) Supplementary Analysis 1 – While on-treatment strategy
	3) Supplementary Analysis 2 – Compliant subjects hypothetical strategy
	4) Sensitivity Analysis – Multiple imputation jump to reference and copy increment from reference
	5) Sensitivity Analysis – Observed data only using narrower visit window for Week 48
Objective	To assess the safety and tolerability of Verdiperstat, relative to placebo, in subjects with MSA
Safety Endpoint	Frequency of unique subjects with serious adverse events (SAEs), AEs leading to study drug discontinuation, AEs related to study drug, clinically significant ECG abnormalities, and clinically significant laboratory test abnormalities
Summary	Number and percentage of subjects with safety events and findings for the safety population
Intercurrent Events	Treatment policy strategy, i.e., no accounting for intercurrent event

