6.4.1 Adverse Events

AEs will be coded using MedDRA and displayed in tables and listings by system organ class (SOC) and preferred term (PT), unless specified otherwise.

Analyses of AEs will be performed for those events that are considered treatment-emergent AEs (TEAEs), where treatment-emergent is defined as any AE that developed, worsened, or became serious on or after first dose of study drug and prior to 30 days after the last dose of study drug.

A TEAE overview without SOC and PT will be presented as the number and percentage of subjects with any of the following TEAEs: TEAE leading to death; serious TEAE; serious TEAE related to study drug; TEAE leading to study drug discontinuation; any TEAE; TEAE related to study drug; and severe AE.

In addition, TEAEs will be tabulated by SOC and PT for all treated subjects for the following endpoints for the DB and OLE phases, separately and combined:

- TEAEs
- TEAEs related to treatment (includes, possibly related and related)
- TEAEs by highest severity (mild, moderate, severe)

- TEAEs related to treatment by highest severity
- Treatment-emergent SAEs
- TEAEs leading to discontinuation of study treatment

In the above tabulations, each subject will contribute only once (i.e., the most related occurrence or the most severe occurrence) to each of the incidence rates in the descriptive analysis, regardless of the number of episodes.

The TEAEs summary by SOC and PT will also include the number of unique AE occurrences; unique occurrences mean that if a subject had an AE twice, both will be reported (i.e., the subject will contribute twice to the count of events).

All AEs occurring pre-treatment and during the entire study will be listed. Additional listings will be provided including deaths, SAEs, AEs leading to discontinuation of study drug, and events of special interest (see Section 6.4.2).

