At Screening, Baseline and Baseline-Extension Only: Urine Drug Screen for cannabis (medical and recreational), amphetamines (including MDMA/ecstasy), cocaine, barbiturate, PCP, benzodiazepines, tricyclic antidepressants, and/or opiates. Reflex confirmatory testing will be conducted on all positive urine drug screen samples.

At Screening Only: Urine alcohol level.

For those participating in the optional CSF sub-study, analysis conducted by local lab of cell counts (white blood cells and red blood cells [with reflexed differential if either of the counts is abnormal], CSF protein and CSF glucose.

Clinical laboratory values will be expressed using conventional and standard international (SI) units with normal ranges provided. In the event of repeat values within the same analysis visit, if any measurement has an abnormal result, that measurement will be used for the presentation in by-visit tables. If none of the measurements are abnormal, or all of them are abnormal, the measurement closest to the target day for the analysis visit interval will be used for presentation in by-visit tables. All measurements will be presented in listings and considered for evaluation of potential drug induced liver injury (DILI) or abnormalities.

On-treatment laboratory abnormalities are those with an assessment date after the date/time of first dose of study drug and within 30 days after the last dose of study drug. For the treatment phase, treatment-emergent laboratory abnormalities will be assessed from the date of first dose of study drug until 30 days after the last dose of study drug.

Clinically significant laboratory abnormalities will be identified as Grade 3 to 4 laboratory test results according to CTCAE version 5.0 if available; otherwise according to DAIDS version 2.1 criteria.

Laboratory Test Change from Baseline

The observed value and change from baseline will be summarized for each continuous laboratory parameter in both conventional and SI units.

Laboratory Test Abnormalities

The number and percentage of treated subjects with at least one on-treatment laboratory assessment will be summarized by treatment group (regardless of baseline) for Grade 0, Grade 1 to 2, Grade 3 to 4, Grade 3, and Grade 4. Note that Grade 3 to 4 abnormalities are considered clinically significant.

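### Safety relative to placebo is a primary estimand, but the protocol and SAP as supplied plan only per-arm counts and percentages for its five components; a risk difference with a 95% interval would be a cheap improvement.

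*Protocol*

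**What the plan says.** Protocol 2.1 names two primary objectives. The second is "To assess the safety and tolerability of BHV-3241, relative to placebo, in subjects with MSA". Protocol 3.1 turns it into an endpoint with five components. Three are adverse-event counts: "The frequency of unique subjects with: serious adverse events; adverse events leading to discontinuation; adverse events judged to be related to study medication". The other two are clinically significant ECG abnormalities and clinically significant laboratory abnormalities.

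SAP 3.2 treats an estimand as the quantity to be estimated for an objective, and names the summary of the endpoint as one of its attributes. SAP Table 1 (3.2.1) fills that attribute in two ways:

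- **Efficacy:** "Difference in mean change from baseline in modified UMSARS scores between treatment groups at week 48 estimated and tested" by MMRM.
- **Safety:** "Number and percentage of subjects with safety events and findings for the safety population". The intercurrent-event entry reads "Treatment policy strategy, i.e., no accounting for intercurrent event" and adds no contrast.

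The analysis sections follow the safety entry:

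- Protocol 9.4.7: "The frequencies of the following safety events are summarized by treatment group and overall for treated subjects".
- SAP 6.4.1: "A TEAE overview without SOC and PT will be presented as the number and percentage of subjects with any of the following TEAEs", followed by tabulations by system organ class and preferred term.
- SAP 6.4.3: "The number and percentage of treated subjects with at least one on-treatment laboratory assessment will be summarized by treatment group", by grade, with Grade 3 to 4 defined as clinically significant.
- SAP 6.4.5: shifts in ECG interpretation, and numbers of subjects beyond QTcF cut-offs.

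**The concern.** The objective is comparative. A percentage in each arm estimates two separate quantities, and the comparison between them is left to the reader. The plan does not treat the same phrase this way elsewhere. The other secondary objectives (PGI-S, CGI-S, UMSARS Parts III and IV) are also worded as relative to placebo, and SAP Table 2 and Section 6.3.1 give them a between-group difference with a standard error, 95% CI and p-value. Those endpoints lie outside the multiplicity control in SAP 5.2, whereas safety is a primary objective.

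The stake is interpretation. With roughly 160 subjects per arm, differences in event percentages are imprecise. Two percentages without an interval can make noise look like a signal. They can also make similar rates look reassuring when a sizeable excess has not been excluded. Protocol 1.4 describes thyroid and uric acid changes with the drug, and an early syncope finding for which a drug effect could not be ruled out. Earlier Phase 2 treatment lasted 8 to 12 weeks, so 48 weeks of placebo-controlled exposure is the main opportunity to quantify an excess.

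**Working it through.** **1. The plan's own figure.** The only sample size calculation (Protocol 9.2, SAP 5.1) concerns efficacy. Inputs: placebo change 4.88, SD 4.85, 40% improvement, 90% power, two-sided alpha 0.05 (Protocol 9.4.5).

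- Difference = 0.40 × 4.88 = 1.952.
- n per arm = 2 × (1.960 + 1.282)² × 4.85² / 1.952² = 129.7, so 130 per arm and 260 in total.
- With 20% drop-out: 260 / 0.80 = 325.

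The figure reproduces. No corresponding figure is stated for safety, so no safety number in the plan is in dispute.

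**2. Where a contrast could appear.**

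| Component (Protocol 3.1) | Planned output | Between-arm estimate or interval |
|---|---|---|
| Serious adverse events | n and % (SAP 6.4.1) | none found |
| Adverse events leading to discontinuation | n and % (SAP 6.4.1) | none found |
| Related adverse events | n and % (SAP 6.4.1) | none found |
| Clinically significant laboratory abnormalities | n and % with Grade 3 to 4 (SAP 6.4.3) | none found |
| Clinically significant ECG abnormalities | interpretation shifts; n and % beyond QTcF cut-offs (SAP 6.4.5) | none found |

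The Kaplan-Meier limits in SAP 6.1.1.1 are for time-to-event endpoints and are not between-arm intervals. None of the five components is defined as time to event. The visible rows of SAP Table 4, which assigns the treatment comparisons, are all efficacy.

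The ECG row has a further gap. SAP 6.4.5 never says which findings are clinically significant, so even the promised count is not fully specified.

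**3. Precision of the missing estimate.** Inputs: 325 randomized 1:1, with nearly all assumed to be dosed, hence about 162 per arm. The documents give no event rates; the rates below are assumptions. For a common rate p, half-width = 1.96 × √(2p(1−p)/162).

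| Assumed rate | 95% half-width (points) |
|---|---|
| 5% | 4.7 |
| 10% | 6.5 |
| 20% | 8.7 |
| 40% | 10.7 |

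**4. An invented example.** Suppose 16/162 (9.9%) on verdiperstat and 8/163 (4.9%) on placebo.

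- Difference = 9.88 − 4.91 = 5.0 points.
- SE = √(0.0988 × 0.9012/162 + 0.0491 × 0.9509/163) = 0.0289.
- Wald 95% CI: −0.7 to 10.6 points.
- Miettinen-Nurminen 95% CI: −0.8 to 11.1 points.

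The data would be compatible with no difference and with a 10-point excess. A table showing 9.9% beside 4.9% displays neither fact.

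**The case against.** The strongest reply is that the summary matches the endpoint. Protocol 3.1 defines the endpoint as a frequency of subjects, and Table 1 summarises that frequency. The objective promises to assess and sets no hypothesis or margin, and a concurrent randomized placebo column is a way of assessing. Descriptive safety tables are common practice. SAP 6.1.2 applies counts and percentages to categorical variables generally, so part of the contrast with efficacy reflects data type. Nothing is biased, no alpha is affected, and a reader can compute an interval from the planned counts. Five unadjusted intervals also carry a risk: if the components were independent, 1 − 0.95⁵ = 23% of trials with no true difference would show at least one interval excluding zero. The components overlap, so the true figure is probably lower.

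Most of this stands, and it limits the point to an improvement. It does not remove the mismatch, because the sponsor made this objective primary, comparative and an estimand, and prespecified no contrast for it.

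A reader might infer more than the documents support:

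- *That no safety contrast will ever be estimated.* SAP 6.4.2 (events of special interest) is not in the supplied text, and the table templates and DMC SAP are separate documents. Events of special interest are not one of the five components, but the statement holds only for the text as supplied.
- *That safety output is one-arm percentages only.* SAP 6.1.1.1 presents both arms, and Section 6.4 also plans changes from baseline, shift tables, ECG interval statistics and an eDISH plot.
- *That every efficacy endpoint gets a difference with an interval.* Some endpoints are redacted, and orthostatic symptoms under UMSARS Part III get only number and percentage (SAP 6.3.3.7).

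**Conclusion.** The point holds as a low-cost improvement. For a primary objective worded as a comparison with placebo, the protocol and SAP as supplied plan no between-arm difference or interval for any of the five components. No stated figure is wrong and the efficacy inference is untouched.

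The size is the uncertainty left undisplayed: about ±4.7 to ±10.7 points over assumed event rates of 5% to 40%. This rests on about 162 treated subjects per arm and on equal rates in the two arms. The rates are illustrative, and widths of this order would arise in any trial of this size. They show why an interval is informative, not that the trial is too small.

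**What to change.** In SAP Table 1 and Section 6.4, for the double-blind phase in the safety population, add to the number and percentage the risk difference (verdiperstat minus placebo) with a 95% Miettinen-Nurminen interval for each of the five components in Protocol 3.1. Label these as estimation, unadjusted for multiplicity, with no p-value and no alpha.

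Before that, state in SAP 6.4.5 which ECG findings count as clinically significant. Without this, neither a count nor a difference can be produced for the ECG component.

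The cost is SAP wording and one extra column in about five tables. No new data, sample size change or change in trial conduct is needed. The downside is about five unadjusted intervals that may be read as tests, which the labelling reduces but does not eliminate.

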2.2 Secondary

Key Secondary

[figure not shown]
- To evaluate the efficacy of BHV-3241, compared to placebo, as measured by the Clinical Global Impression of Improvement (CGI-I) score at Week 48.
- To evaluate the impact of BHV-3241 on quality of life, compared to placebo, as measured by a change from baseline in the motor subscale of the MSA-Quality of Life (MSA-QoL) scale at Week 48.
- To evaluate the impact of BHV-3241 on quality of life, compared to placebo, as measured by a change from baseline in the non-motor subscale of the MSA-QoL scale at Week 48.

- To evaluate the efficacy of BHV-3241, compared to placebo, as measured by a change from baseline in the UMSARS Part I and Part II total score at Week 48.

Other Secondary

- To assess the impact of BHV-3241, relative to placebo, as measured by a change from baseline at Week 48 in the following instruments:
 - Patient Global Impression of Severity (PGI-S),
 - Clinical Global Impression of Severity (CGI-S),
 - UMSARS Part III,
 - UMSARS Part IV.

CCI

CCI

3 STUDY ENDPOINTS

3.1 Primary

- Change from baseline in a modified UMSARS score, based on a subset of items from Part I and II, at Week 48 (see Section 9.4.2).
- The frequency of unique subjects with: serious adverse events; adverse events leading to discontinuation; adverse events judged to be related to study medication; clinically significant ECG abnormalities and clinically significant laboratory abnormalities.

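### The laboratory part of the primary safety endpoint counts on-treatment Grade 3–4 values without regard to baseline grade; the effect is probably small and one derived flag removes it

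*Protocol*

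**What the plan says.** - **Endpoint.** Protocol 3.1 (Primary) lists, among other components, subjects with "clinically significant ECG abnormalities and clinically significant laboratory abnormalities". It states no baseline condition. The matching objective (Protocol 2.1) is safety relative to placebo.
- **Summary.** SAP Table 1 (section 3.2.1) gives the summary as "Number and percentage of subjects with safety events and findings for the safety population". It names no source table and no test.
- **Grade.** SAP 6.4.3: "Note that Grade 3 to 4 abnormalities are considered clinically significant". Protocol 6.2.2.4 uses the same definition.
- **Count.** SAP 6.4.3 says the number and percentage of treated subjects "will be summarized by treatment group (regardless of baseline"), with grade bands that include Grade 3 to 4, Grade 3 and Grade 4.
- **Windows.** SAP 6.4.3: "On-treatment laboratory abnormalities are those with an assessment date after the date/time of first dose of study drug and within 30 days" of the last dose. The next sentence says that "treatment-emergent laboratory abnormalities will be assessed from the date of first dose of study drug until 30 days after the last dose". Neither sentence requires a change from baseline.
- **Contrast with adverse events.** SAP 6.4.1 defines a treatment-emergent adverse event as "any AE that developed, worsened, or became serious on or after first dose of study drug", up to 30 days after the last dose.
- **Baseline-referenced displays.** SAP 6.4.3 also plans shift tables by grade, by visit and to the overall minimum and maximum, for subjects with both a baseline and an on-treatment value.

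**The concern.** The endpoint is meant to describe what happens on drug compared with placebo. A subject who enters with a Grade 3–4 value and still has it after dosing tells us nothing about the drug, yet counts as an event. Such subjects add a similar background to both arms, which pulls the risk ratio towards 1 and the risk difference slightly towards 0. A chance imbalance in them between arms would appear as a treatment difference in that count. The adverse-event components of the same endpoint are counted as new or worsened, so one primary endpoint mixes two standards of attribution.

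The treatment-emergent sentence does not close the gap. It has no worsening condition and no table is tied to it. Its window opens on the date of first dose, whereas the on-treatment window opens after the date and time of first dose. Baseline laboratory samples are scheduled pre-dose on Day 1 (Protocol Table 1), the day of the first dose. Read literally, the baseline sample can fall inside the treatment-emergent window, although SAP 7.1 classes it as pre-treatment.

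**Working it through.** **The plan's own figure.** The plan sizes only the efficacy endpoint. The difference is 0.40 × 4.88 = 1.952 points; n = 2 × (1.960 + 1.282)² × (4.85/1.952)² ≈ 130 per group, so 260 in total; 260/0.80 = 325. This reproduces Protocol 9.2 and SAP 5.1. It matters here only for arm size: 325/2, about 162 per arm.

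**Which subjects are counted.** Under SAP 6.4.3:

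1. Grade 3–4 before dosing, lower grade at every on-treatment sample: not counted.
2. Grade 3–4 before dosing, and still or again Grade 3–4 on treatment: counted.
3. Lower grade before dosing, Grade 3–4 on treatment: counted.

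Only group 2 is at issue. Those whose grade rises from 3 to 4 have genuinely worsened and should stay in the count.

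**Inputs.** The documents give neither a baseline Grade 3–4 prevalence nor an on-treatment rate. The following are assumptions:

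- b = share of each arm with Grade 3–4 carried over from baseline: 1%, 2%, 5%.
- p = rate of new Grade 3–4 among the others: 5% on placebo, 10% on active.

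**Formulae.** Counted rate = b + (1 − b)p. Counted risk difference = (1 − b)(p_active − p_placebo). Subjects carried in per arm = 162b.

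| b | Placebo | Active | Risk difference (points) | Risk ratio | Carried in per arm |
|---|---|---|---|---|---|
| 0 | 5.00% | 10.00% | 5.00 | 2.00 | 0 |
| 1% | 5.95% | 10.90% | 4.95 | 1.83 | 1.6 |
| 2% | 6.90% | 11.80% | 4.90 | 1.71 | 3.2 |
| 5% | 9.75% | 14.50% | 4.75 | 1.49 | 8.1 |

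Example at b = 5%: placebo 0.05 + 0.95 × 0.05 = 0.0975; active 0.05 + 0.95 × 0.10 = 0.145; ratio 0.145/0.0975 = 1.49.

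With assumed rates of 5% and 15%, the risk difference falls from 10.0 to 9.9 (b = 1%) and 9.5 (b = 5%), and the risk ratio from 3.00 to 2.66 and 1.97.

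**Chance imbalance.** The SD of the between-arm difference in carried-over subjects is √(2b(1 − b)/162). At b = 2% this is √(0.0392/162) = 0.0156, or 1.6 points, equal to 2 to 3 subjects (162 × 0.0156 = 2.5).

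The absolute difference hardly moves; the ratio moves more. Power is not shown because no test is planned for this component.

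**The case against.** The case for leaving the SAP alone has four parts.

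1. **Eligibility.** A reader might infer that analytes without a numeric limit, such as CPK, GGT, ALP and electrolytes, are unrestricted at entry. They are not. Exclusion 3a (Protocol 5.3) bars clinically significant laboratory deviations in general, except those in keeping with the target population. Numeric limits also cover ALT, AST, bilirubin, creatinine, eGFR, haematology, HbA1c, and abnormal free T4 combined with TSH above 10. This stands: baseline Grade 3–4 should be uncommon, and nothing in the documents supports a carry-over as high as 10%. It need not be zero, given the target-population qualifier and a screening period of up to 42 days.

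2. **Existing displays.** A reader might infer that no baseline-referenced view exists. The shift tables by grade provide one. Protocol 8.2.2 also sends clinically significant laboratory results to the adverse-event forms, where the new-or-worsened rule applies. This stands, with a limit. The endpoint counts unique subjects. If the shift tables are per test, their cells cannot be added to give that number, and they omit subjects without a baseline value. The adverse-event tables count reported terms, not Grade 3–4 values.

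3. **The link to Table 1 is inferred.** True. SAP Table 1 does not name the table, and Protocol 9.4.7 mentions a by-arm frequency without a baseline rule. Apart from cells of the shift tables, though, the SAP specifies no other by-arm count of subjects with Grade 3–4 values. It also does not say whether that table pools analytes; if it is per analyte, b for each analyte would be smaller than any pooled b.

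4. **An inclusive count is a legitimate choice.** It is, as a supportive display. It is less suitable as the count behind an endpoint defined relative to placebo.

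**Conclusion.** The gap in definition is real and its effect is probably small. Under SAP 6.4.3, Grade 3–4 values that precede dosing and persist or recur on treatment count as events, while adverse events in the same endpoint must be new or worsened. With assumed new-onset rates of 10% and 5% and an assumed carry-over of 1–5%, about 2 to 8 subjects per arm are carried in. The risk difference falls from 5.0 to 4.95–4.75 points and the risk ratio from 2.00 to 1.83–1.49.

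Two stronger readings are not supported. One is that any abnormality before dosing becomes an event: it must also be Grade 3–4 in a sample inside the on-treatment window. The other is that the rule conceals a drug effect or weakens a test: the component is descriptive, no alpha or power attaches to it, and the shift tables show baseline grade. This is a worthwhile low-cost improvement, not a flaw that threatens the safety conclusions.

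**What to change.** 1. In SAP 6.4.3 and Table 1, define the laboratory event for the primary safety endpoint as an on-treatment Grade 3–4 value whose grade is higher than the subject's baseline grade for the same analyte and direction. Use the baseline definition in SAP 6.2.5 and treat a missing baseline as Grade 0, which is in line with the worst-case rule for adverse-event dates in SAP 6.1.3.
2. Name in Table 1 the output that supplies this count, and state that each subject is counted once across analytes.
3. Add the same new-or-worsened condition to the treatment-emergent laboratory definition, and start its window after the date and time of first dose so that it agrees with the on-treatment definition.
4. Keep the present table, which ignores baseline grade, as supportive.

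The cost is SAP wording and one derived flag; no new data are needed. The count becomes slightly smaller in both arms. Making the change before unblinding avoids a later choice between two counts.
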